### **3.2.2 Information on Adverse Effects**

In accordance with the study follow-up plan procedures (Chapter 2.5.8 Safety Assessment and Control; Chapter 2.5.9 Schedule of Study Visits and its Appendix 4. and Section 2.6 Evaluation of Study Outcomes), all study subjects will undergo a medical examination, routine, conventional laboratory and instrumental examinations, and adherence to the treatment will be assessed. Results of clinical and laboratory examinations and treatments performed outside the study center and the study protocol will be reviewed (see Chapter 2.5.2 Randomization and Treatment Procedures; Chapter 2.5.8 Safety Assessment and Control). These results will allow for the assessment of significant adverse events and effects.

Information on the results of medical care provided outside the study center (medical record) will be retrieved by the investigator and recorded in a special form for recording adverse effects.

### **3.2.3 Recording and Assessing Adverse Effects**

All observable and voluntary adverse events ("serious" or "non-serious") and abnormal test results during the study, regardless of treatment intervention arm allocation and presumed causal relationship or relationship to the investigational product or other therapeutic agent or diagnostic test, will be recorded in the study data registration form.

Information on the volume and purpose necessary to describe and evaluate all adverse events will be obtained from the study site or outside the study site and collected from the study subject's observation procedures, including diagnostic and therapeutic procedures. The volume and content of the information obtained from the adverse event or abnormal test result should ensure:

- Identification of possible clinical outcomes;
- Classification of severity and randomness;
- Establishing a causal relationship
  - to the investigational product;
  - to a disease/concomitant, or comorbid condition;
  - to other therapeutic or diagnostic agents;

An adverse effect or abnormal test result, whether related to the investigational product, another therapeutic agent, or a disease/concomitant or comorbid condition, will be followed up until it resolves or stabilizes to a level acceptable to the investigator or medical team.

### **3.2.4 Abnormal Test Results**

An individual abnormal result of a study alone cannot be considered an adverse event. An abnormal result of the study is classified as an adverse event if it meets one or more of the following criteria:

- accompanied by relevant clinical symptoms;
- requires specific diagnostic evaluations, or therapeutic measures, such as surgical intervention, or additional drug or non-drug treatment, which is not recommended and considered for the treatment of the disease/condition of study interest and provided in the framework of study procedures;
- an effect changes or terminates the treatment intended for the study or the conditions of participation of the study subject (for example, when an abnormal study result determines the study exclusion criteria);
- considered as an adverse event by the sponsor or investigator of the study;

### **3.2.5 An Event Causality Assessment**

The investigator shall review a described and documented adverse event or abnormal study result if:

- The abnormal study result is classified as an adverse event;
- There is a proven relationship between the adverse event to the use of the investigational product or the study drug treatment;
- Meets the definition of a MACCE or AAME.

In such circumstances, the adverse event or abnormal study result is recorded in the patient's medical record, the study data collection form, and reported to the principal investigator and the study sponsor for review. The adverse event or abnormal study result is monitored and managed by the patient's medical care team.

In cases when the causality is initially determined by the investigator or sponsor as "unknown but unrelated to the investigational product or study treatment," it is recorded in the patient's medical record and the study data registration form with appropriate explanations. The patient's medical care team will continue to monitor and respond to it.

In cases where the causality will be assessed by the investigator or the study sponsor, as MACCE or AAME, even if there is a probable or doubtful relationship with the disease/condition of study interest or the investigational product, the adverse event/effect will still be classified as associated with the disease/condition or investigational product. The patient's medical care team will continue to monitor and respond to the adverse event/effect. The concluded results will be recorded in the study data registration form following assessments and the health care team discussions.

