### 3.2 Adverse Event Reporting

#### 3.2.1 Definition of an Adverse Event

**Major Adverse Cardiovascular and Cerebrovascular Events (MACCEs):** A clinically significant adverse cardiovascular and cerebrovascular clinical event that occurs in CAD cases, which may be recurrent, incidental, with a frequency consistent with that expected in the course of the disease and the natural history of the disease (Hazard Ratio [HR], 1.26–5.68, 95%CI [4,5,7,18,23]), is quite common (1–10%) in terms of its probability, is severe in terms of its outcome, is associated with the impact of the risks associated with the disease even under optimal management, is clinically serious, may lead to death, may change the course of the disease/clinical condition, and is not preventable. MACCE determines the outcome of the clinical cases in the study and is, therefore, considered a study clinical endpoint. These include: Cardiovascular death, Nonfatal myocardial infarction, Recurrent angina, Stent thrombosis, Repeated PCI, CABG, Ischemic stroke, Transient ischemic attack, Intracerebral hemorrhage, Atrial fibrillation, Heart failure.

**Anticipated Adverse Medication Effect (AAME):** A serious adverse effect on the patient's health or a life-threatening problem or death associated with a medicinal product, in cases where the cause of the clinical effect, problem or death is already established and is consistent with previously studied possible effects of the medicinal product in its nature, severity or frequency of occurrence; an expected serious problem with the medicinal product that is related to the safety of the study participant. Possible adverse effects associated with treatment with clopidogrel, prasugrel, or ticagrelor are expected and are considered clinical outcomes and are considered clinical endpoints of the study: Bleeding requiring hospitalization, Thrombotic thrombocytopenic purpura, Minor or minimal bleeding, Change/discontinuation of P2Y12 inhibitor.

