### **3.2.7 Adverse Event Reporting to the IRB**

Any adverse event that is assessed as MACCE or AAME will be reported by the investigator or sponsor to the IRB of the study center, along with a description and an analysis of the adverse event. The IRB will review the reported adverse event, evaluate it, and make recommendations for further clinical trial follow-up or withdrawal of the subject from the study.

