## 6.0 Informing the IRB

The study protocol, the participant consent form and, upon request, all documents regulating the study activities and procedures approved by the Medical Ethics Board will be submitted to the study center's IRB.

All documents issued by the IRB will be kept throughout the study period, along with other study documents. Through them, the investigator will receive confident evidence of compliance with existing regulations of the study procedures.

Throughout the study period, any MACCE, UAME, and all observable or voluntary adverse clinical events will be reviewed by the study center's IRB. It will review these events and, if necessary, present a position on ethical issues of study case management.

Before the start of the study, the investigator must have a written study protocol and informed consent form approved by the IRB, which will then be used to initiate the activities envisaged by the study.

If changes to the protocol and informed consent form are necessary, they will not be used in the research process until the IRB has reviewed the changes, if necessary, with the participation of the study sponsor, eliminated provisions containing risks to the study participant, and approved the changes to the documents in written form.

In addition to making changes, updates or additions to the research protocol and informed consent form, the IRB should, as necessary, review, indicate to the study sponsor, and amend other previously received documents that may be affected by the changes to the research protocol and informed consent form.

The IRB may request revisions to the protocol or other research documentation if content received from various information channels will be related to risks for study conducting activities or present conditions

that may affect study participant's safety. In addition, the IRB may require an annual review of research documents for the purpose of updating them or completing the study.

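### Section 3.2.7 gives no IRB report for an unexpected drug reaction although section 6.0 promises IRB review, and section 3.2.5 gives no direct sponsor report for a serious one that is suspected but not proven

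*Combined protocol and SAP*

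**What the plan says.** Section 3.2.1 (Definition of an Adverse Event) defines two classes. MACCE covers the cardiovascular and cerebrovascular events expected from the disease. AAME covers serious drug effects whose cause "is already established and is consistent with previously studied possible effects of the medicinal product".

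Section 3.2.3 requires all events, serious or not, to be recorded "regardless of treatment intervention arm allocation and presumed causal relationship".

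Section 3.2.5 (An Event Causality Assessment) lists three circumstances in which the investigator reviews an event and it is reported to the principal investigator and the sponsor. The first is an abnormal test result that has been classed as an adverse event. The second is a causal link, worded as follows: "There is a proven relationship between the adverse event to the use of the investigational product or the study drug treatment". The third is that the event belongs to one of the two defined classes, MACCE or AAME.

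An event initially judged to be of unknown cause, but not related to the product or study treatment, is recorded and managed; no report is mentioned.

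Section 3.2.7 sets the IRB rule: "Any adverse event that is assessed as MACCE or AAME will be reported by the investigator or sponsor to the IRB".

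Section 6.0 (Informing the IRB) is wider. It says that "any MACCE, UAME, and all observable or voluntary adverse clinical events will be reviewed" by the IRB of the study centre. UAME appears only there and is not defined.

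**The concern.** Safety reporting exists mainly to bring unforeseen harm quickly to people who can act on it. Here the direct reports are built around foreseen events. An unexpected drug reaction cannot be an AAME by definition, so section 3.2.7 never calls for an IRB report of it.

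The causality threshold in section 3.2.5 is also uneven. A MACCE or AAME is still classed as associated when the link is only probable or doubtful, while an event outside those classes needs a proven link unless it is an abnormal test result. A drug link can rarely be proven from a single case. Seriousness is not a trigger: SAE is in the abbreviation list, but sections 3.2.5 to 3.2.7 contain no SAE criterion.

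What is at stake is the IRB's ability to do what the protocol asks of it. Section 2.6.4 gives the IRBs oversight of participant safety, and section 3.2.7 relies on the IRB to advise on a participant's further follow-up or withdrawal. It cannot advise on events that it is not sent. A site also cannot tell whether section 3.2.7 or section 6.0 sets its duty.

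**Working it through.** No arithmetic applies; the check is a comparison of the rules. By *unexpected reaction* I mean a suspected drug reaction that is neither a MACCE nor an AAME. Section 3.2.5 puts neither *and* nor *or* between its three triggers. I read them as alternatives, which is the more generous reading.

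| Serious unexpected reaction | Investigator report to sponsor (3.2.5) | Report to IRB (3.2.7) | Monitoring route to sponsor (2.6.4, 4.0) | IRB review promised (6.0) |
|---|---|---|---|---|
| (a) link proven | yes | none | yes | yes |
| (b) link suspected, not proven; not an abnormal test result | none | none | yes | yes |
| (c) abnormal test result classed as an adverse event | yes | none | yes | yes |

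**IRB.** The section 3.2.7 column is empty in every row and the section 6.0 column is filled in every row. The conflict does not depend on causality. Nor does it depend on what UAME means. UAME may be a slip for AAME, because section 3.2.6 uses a very similar phrase with AAME in that position. If so, section 6.0 still goes on to promise review of adverse clinical events beyond the named classes, and section 3.2.7 still supplies no report of them.

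**Sponsor.** The gap is row (b) only. Row (c) is fairly wide: under section 3.2.4 an abnormal result counts if, among other criteria, it is "considered as an adverse event by the sponsor or investigator of the study". That section covers test results, however, not reactions seen only clinically.

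**Section 3.2.6** does not fill either gap. It is written around MACCE and AAME, its wording is unclear, and it names no report to the sponsor or IRB.

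**Monitoring.** Section 4.0 includes reporting of adverse events to the sponsor without limit by type or causality, and section 2.6.4 adds regular reports to the sponsor. Planned site monitoring takes place every 4 to 6 weeks. Where section 4.0 lists the risk cases to be assessed, the clinical classes it names are again abnormal results, MACCE and AAME. Nothing in section 4.0 forwards events to the IRB.

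**The case against.** The strongest reply is that the protocol has several safeguards beyond section 3.2.5. Every event is recorded and followed until it resolves or stabilises (3.2.3). The principal investigator reviews and signs every data record form (7.1). Adverse-event reporting is a critical monitored process, serious or not (4.0). The sponsor receives regular monitoring reports (2.6.4). Early withdrawal needs a stated justification and an analysis of the reason (3.3), and is itself monitored (4.0). The judgement that an event is unrelated may be the sponsor's own. The study also uses no new drugs.

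Much of this stands, and it rules out several stronger readings that a reader might infer:

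- *That an unexpected reaction never reaches the sponsor, or goes no further than the site.* Rows (a) and (c) are reported directly, and monitoring covers row (b).
- *That no one outside the site would review it.* Section 2.6.4 describes monitors who are not directly involved in carrying out the research.
- *That the safety conclusions would rest only on event types fixed in advance.* Section 3.2.3 keeps all events in the data.
- *That section 6.0 contradicts the sponsor rule.* Section 6.0 concerns IRB review, so it conflicts only with section 3.2.7.

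The reply does not close the gap. Monitoring is periodic; it is not an investigator's duty to report an event when it occurs. None of these routes is a stated report to the IRB.

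**Conclusion.** The concern holds in two parts. First, sections 3.2.7 and 6.0 conflict on what reaches the IRB: an unexpected reaction has no stated IRB report, even with a proven link. This follows from the text alone. Second, section 3.2.5 has no direct investigator-to-sponsor report for a serious unexpected reaction that is suspected but not proven, unless it appears as an abnormal test result classed as an adverse event. This rests on reading the three triggers as alternatives; read as joint conditions, the direct report would be narrower still.

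The size cannot be put as a number. All 240 participants fall under these rules, but the documents give no frequency for unexpected reactions. A probability of seeing at least one such reaction in an arm would rest on an assumed frequency, and would measure occurrence rather than failure to report.

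This is an internal inconsistency and a missing direct reporting line. It is not a loss of safety data.

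**What to change.** - Reconcile sections 3.2.1, 3.2.5, 3.2.6, 3.2.7, 4.0 and 6.0, so that one rule states what goes to the sponsor and what goes to the IRB.
- In section 6.0, either correct UAME to AAME if it is a slip, or define it in section 3.2.1. The sponsor should settle the intended meaning before adding a class.
- In section 3.2.5, replace the requirement for a proven relationship with *a relationship cannot be excluded*.
- Add serious adverse events that are neither MACCE nor AAME, whatever the causality judgement, to the direct sponsor report in section 3.2.5 and the IRB report in section 3.2.7.

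The cost is wording and a few more reports. The events are already recorded under section 3.2.3, so no new data collection is needed, and no treatment rule changes.

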### **3.2.6 Adverse Event Reporting**

Any MACCE or AAME observed or voluntary adverse event occurring in a trial is identified by the investigator or sponsor. Information about it is submitted to the trial participant's medical care team, who should then direct the clinical case management.

A MACCE or AAME event is recorded:

- In the study data registration form;
- A description and significance of the event are recorded in the routine medical documentation;

After the registration of the MACCE or AAME event, the participant will be withdrawn from the study.

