## **2.6 Evaluation of Study Results**

### **2.6.1 Study Endpoints**

The study follow-up results will be discussed and presented by study arms, as well as concerning the primary and secondary endpoints of the study.

The study results will also be discussed concerning other endpoints, which will be represented by clinical or non-clinical data and characterize the factors that affect the efficacy of antiplatelet treatment and determine the clinical and non-clinical outcome in the course of the CCSs both with and without the results of CYP2C19 genotyping.

The indicators for assessing the effectiveness of the study are presented in Appendix 5.

In the study, the selection of treatment regimens with clopidogrel and an alternative P2Y12 inhibitor will be carried out by determining the genotype of the CYP2C19 \*2, \*3 non-functional alleles. Clopidogrel will be used in study participants with CYP2C19 \*2, \*3 normal allele genotypes and in the control arm of study participants not undergone CYP2C19 genotyping – unspecified CYP2C19 genotype. Study participants with CYP2C19 \*2, \*3 non-functional allele genotypes will be given alternative antiplatelet therapy.

In cases of CAD, regardless of treatment with P2Y12 inhibitors after ePCI, the clinical endpoints will be represented with MACCEs and other clinical conditions related to CAD or the potential adverse events of antiplatelet drug treatment. The incidence of the primary, secondary and other study endpoints defined as clinical outcomes of CYP2C19 genotype-guided P2Y12 inhibitor treatment will be assessed in the study arms.

The primary endpoints of the study are defined as:

- Number of study participants who died from any cause (Death from Any Cause) within a 12-month of the study follow-up;
- Number of study participants who died from any cardiovascular cause (Death from Cardiovascular Cause) within a 12-month of the study follow-up;

The secondary endpoints of the study are defined as:

- Number of study participants who experienced non-fatal myocardial infarction (Non-fatal Myocardial Infarction) within a 12-month of the study follow-up;
- Number of study participants who experienced unstable angina or angina requiring hospitalization (Unstable Angina) within a 12-month of the study follow-up;
- Number of study participants who experienced a stroke or transitory cerebral ischemic event (Stroke or TIA) within a 12-month of the study follow-up;

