## **3.3 Early Withdrawal of a Study Participant**

A study participant may withdraw from the study at any time during the study and for any reason, whether identifiable or not, by their own free will. This decision and the patient's independent choice are presented in the informed consent form.

A study participant may also be withdrawn early from the study if there is persistent non-adherence to the study follow-up and treatment procedures (see Chapter 2.5.6, Withdrawal from the Study Due to Non-Adherence to Treatment).

A study participant may be withdrawn early from the study based on a clearly stated justification by the investigator or the study sponsor if it is in the patient's best interests to discontinue the study.

The basic reasons for withdrawal from the study are considered as follows:

- If any abnormal study result, symptom, or measurement parameter is detected and resolution, improvement, correction or stabilization of which may require a long period of treatment and/or observation and will change the course of the study-defined follow-up and treatment;
- Any adverse event that may persist during the follow-up period, or require a change or discontinuation of the study-defined treatment, or disrupt the study-defined clinical evaluation plan, or be associated with a severe outcome.
- Any adverse event that may be masked by the use of different medical care regimens than those specified in the study protocol;
- If study treatment intervention, it may pose an expected AAME, a health threat, requiring discontinuation and modification. These conditions require modified treatment measures and regimens other than those specified in the study, including hospitalization. In addition, clinical conditions that may be characteristic of AAME may be exclusion criteria from the study.
- An adverse event related to treatment with P2Y12 inhibitors is a study endpoint, after which the study-planned follow-up is no longer required.
- The MACCE determines the study endpoint, and further measures are no longer required.

In these cases, study participants are discontinued from the study-planned follow-up; the necessary assessments of early withdrawal from the study should be conducted, and the reason for early withdrawal from the study should be determined (evaluated). In these cases, the patient continues to be monitored and treated by the medical support team.

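### Sections 3.2.6 and 3.3 end study follow-up after a MACCE or AAME, and nothing then requires vital status at month 12, so later deaths can be missed in both primary endpoints

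*Combined protocol and SAP*

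**What the plan says.** Section 2.6.1 and the Synopsis name two primary endpoints, all-cause and cardiovascular death. The first reads: "Number of study participants who died from any cause (Death from Any Cause) within a 12-month of the study follow-up".

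Section 3.2.6 sets the rule for what happens after an event: "After the registration of the MACCE or AAME event, the participant will be withdrawn from the study". Section 3.3 gives the reasons: "The MACCE determines the study endpoint, and further measures are no longer required" and, for drug-related events, "An adverse event related to treatment with P2Y12 inhibitors is a study endpoint, after which the study-planned follow-up is no longer required". It states the consequence as: "In these cases, study participants are discontinued from the study-planned follow-up". The medical team continues clinical care.

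Section 3.2.1 lists the MACCEs: "Cardiovascular death, Nonfatal myocardial infarction, Recurrent angina, Stent thrombosis, Repeated PCI, CABG, Ischemic stroke, Transient ischemic attack, Intracerebral hemorrhage, Atrial fibrillation, Heart failure". It says a MACCE "is quite common (1–10%) in terms of its probability", with no time period. An AAME is described as "an expected serious problem with the medicinal product that is related to the safety of the study participant", but its list also includes minor bleeding and a change of P2Y12 inhibitor. No AAME rate is given.

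After early withdrawal, the Synopsis (Follow-up) requires one evaluation within 72 hours, and the Appendix 2 schedule has one withdrawal column. Section 3.2.3 follows an adverse effect until it resolves or stabilizes. Section 3.3 provides for the use of data collected before withdrawal, and section 3.4 allows a withdrawn participant's study period to be shorter than 12 months.

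**The concern.** Stopping at the first MACCE would suit a trial whose only endpoint was time to that event. Here the primary outcome is death, and most of the triggers leave the participant alive and able to die before month 12. The triggering event is recorded; a death after it need not be.

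The participants affected are not a random subset: each has just had a cardiovascular or drug-related event. If such events raise the risk of death, the loss is informative, and the death rates, relative risk, relative benefit and absolute benefit in Appendix 3 are no longer 12-month incidences. No analysis can recover deaths that were not collected.

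**Working it through.** **Does any section close the gap?** These are the places that could.

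| Place | What it provides | Vital status at month 12 after withdrawal? |
|---|---|---|
| Synopsis, Follow-up; Appendix 2 | One evaluation, within 72 hours | No |
| 2.3.2 | All cases followed at 3, 6 and 12 months | Withdrawn participants not addressed |
| 2.4.2 | Assessment of some dropouts, at interim periods or at withdrawal | No |
| 3.2.2 | Investigator retrieves information on care given elsewhere | Withdrawn participants not named |
| 3.2.3 | Event followed to resolution or stabilization | No |
| 3.2.7 | IRB may recommend further follow-up or withdrawal | Case by case only |
| 4.0 | Collection of outside-care results is monitored, with site visits every 4-6 weeks | Withdrawn participants not named |
| 7.1 | Medical record covers the whole study; omitted data are checked | Record may show a death, but no month-12 check is required; visits cancelled by withdrawal not mentioned |

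None requires it.

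**Do the sections agree?** No. Sections 3.2.6 and 3.3 withdraw after a MACCE or AAME. The Synopsis and 2.4.2 each give four reasons for withdrawal or non-completion (participant's choice, non-compliance, loss to follow-up, physician's decision), and neither names a MACCE or AAME. Section 3.2.7 leaves further follow-up open, and 2.3.2 follows all cases.

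**What does the analysis do with an uncollected death?** The Appendix 3 death rates divide by all participants in the arm, so an unrecorded death is in effect survival. The relative-risk rows divide by dead plus not dead, with no place for unknown status. Section 2.6.3 gives no rule.

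**Size.** The plan gives no figure for missed deaths, so there is nothing to reproduce; this is an illustration.

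Inputs from the documents: N = 240 (2.6.2) and MACCE frequency Q = 1-10% (3.2.1), read here as a 12-month risk. Assumptions not in the documents: 12-month mortality of 2% without a trigger, constant hazards, and a post-event death hazard k = 1, 3 or 5 times baseline.

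With time in years, m = -ln(0.98) = 0.0202 and L = -ln(1 - Q).

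- Deaths before any trigger (counted) = 240 × m/(L+m) × [1 - e^-(L+m)]
- Deaths after a trigger (can be missed) = 240 × ∫₀¹ L e^-(L+m)t [1 - e^-km(1-t)] dt

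Example, Q = 10%: L = 0.1054 and L+m = 0.1256. Counted = 240 × 0.1609 × 0.118 = 4.56. At k = 5 the integral gives 1.18 missed, so the total is 5.74 and the missed share is 20.6%.

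| Q | k = 1 | k = 3 | k = 5 |
|---|---|---|---|
| 1% | 0.02 of 4.80 (0.5%) | 0.07 of 4.85 (1.5%) | 0.12 of 4.89 (2.4%) |
| 5% | 0.12 of 4.80 (2.5%) | 0.36 of 5.04 (7.1%) | 0.59 of 5.27 (11.1%) |
| 10% | 0.24 of 4.80 (5.1%) | 0.72 of 5.28 (13.7%) | 1.18 of 5.74 (20.6%) |

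Sensitivity at Q = 10%:

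- If all baseline deaths are cardiovascular and already inside Q, L = 0.1054 - 0.0202 = 0.0852, and missed deaths fall to 0.20 of 4.80 (k = 1) through 0.96 of 5.57 (k = 5), or 4.1-17.3%.
- Baseline mortality of 1% or 5% at k = 5 gives 0.60 of 2.88 (20.9%) or 2.83 of 14.22 (19.9%).
- Fixing the death risk after an event directly can give more. With 1% dying as the first event, 10% having a non-fatal event and 20% of those then dying (all assumed), 240 × 0.10 × 0.20 = 4.8 of 2.4 + 4.8 = 7.2 deaths are missed (67%).

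**The case against.** The best defence is that a later death would probably surface. Outside care is to be retrieved, that process is monitored, the medical record runs through the whole study, and Appendix 3 plans incremental costs in cases with MACCEs, which suggests some data collection after the event. This stands in part: it narrows the gap. But none of it expressly covers withdrawn participants or month 12, and 3.3 says study-planned follow-up has ended. The four stated withdrawal reasons can also be read to mean that a MACCE is not a withdrawal at all; that shows a contradiction and does not supply a collection rule.

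Several stronger readings are tempting, and the documents do not support them.

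- *Post-withdrawal data are barred.* Section 3.3 provides for use of earlier data; it does not exclude later data.
- *One arm is favoured.* No event or withdrawal rates by arm are given, so no direction of bias can be claimed.
- *The composites lose their events too.* A participant withdrawn for MI or stroke is already counted in MACCE and NACE. Only triggers outside those composites, such as angina, atrial fibrillation or heart failure, put them at risk.
- *The Cox model will be informatively censored.* Section 2.6.3 names Cox regression without a censoring rule, and Appendix 3 calculates its hazard rates as proportions, so what would be done is unknown.
- *The 25% not expected to complete (2.4.2) measures this loss.* That figure covers non-completion for the four other reasons.
- *Repair will be impossible.* Electronic identifiers are deleted once data collection ends, but a hard copy is kept for one year (7.1) and the sponsor keeps the coding list (7.2).

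**Conclusion.** The concern holds and should be fixed before the plan is relied on. Followed as written, the plan stops requiring its own primary outcome after a MACCE or AAME, and the Appendix 3 denominators then treat any unrecorded death as survival. This rests on the text and does not depend on the illustrated counts.

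Under the stated assumptions about 0.02 to 1.2 of about 4.8 to 5.7 deaths (0.5-21%) could be missed. Fewer would be missed to the extent that cardiovascular deaths are already inside the 1-10%; more would be missed through AAME withdrawals, which have no stated rate and are left out. The range is not an upper bound. The absolute numbers are small, but with about five deaths expected in the whole trial under these assumptions, one missed death would matter.

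**What to change.** 1. In 3.2.6 and 3.3, state that ending study visits after a MACCE, an AAME or another investigator-initiated withdrawal (2.4.4 for diabetes control, 2.5.6 for non-adherence) does not end collection of the primary outcome. Vital status and, if the participant has died, date and cause of death are obtained at month 12 by visit, telephone or medical record for every randomized participant, unless consent for this is withdrawn.
2. Amend the data-use paragraph of 3.3, section 3.4 and the Appendix 2 schedule to match, and complete the check before the identifiers are destroyed (7.1).
3. In 2.6.3, state how unknown month-12 vital status enters the Appendix 3 rates and relative risks, and report the number unknown in each arm.
4. Reconcile the Synopsis (Follow-up), 2.3.2, 2.4.2, 3.2.6, 3.2.7 and 3.3 on whether and how a MACCE or AAME ends participation. That decision belongs to the sponsor and investigators; no clinical rule is proposed here.

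The cost is a call or record check for about 2 to 24 participants with a MACCE (1-10% of 240), plus those withdrawn for an AAME or by the investigator for other reasons, and an IRB-approved amendment (6.0).
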